### **Additional Cohort of Non-Randomized Patients**

As noted above in the Overview, after the initial 48 patients have been enrolled in the randomized portion of the trial, 20 additional patients with metastatic disease will be enrolled into Arm C in order to further characterize tumor response of R848. These patients will not be included in the primary analysis. Tumor response as measured by a 50% shrinkage in tumor size by irRC criteria will be the primary endpoint for these patients. The response rate associated with the standard of care in these patients is no more than 5%. We expect a total of 10 metastatic disease patients in Arm A from the initial randomized portion of the trial. Combined with the additional 20 patients (Arm A and C, with a total of 30 patients, we will have 82% power to detect an increase to 22%, assuming a one-sided exact binomial test with a 5% Type I error rate.

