Blood samples will be obtained serially in order to determine the immune response against the gp100(g209-2M) and MAGE-3 vaccines (weeks 0, 2, 4, 8, 12, 16, 20, and 24: weeks 8 and 16 will not be collected when leukapheresis is performed; blood samples will be collected by leukapheresis at weeks 0 and 8 (+/- 1 week), and 16 when feasible). To evaluate the inflammatory infiltrate at the site of immunization, biopsies will be obtained of vaccination sites as outlined in section 7.3

Subjects in the adjuvant cohort.

Vaccination will continue for the designated 8 weeks. Blood draw and pheresis times will be the same as subjects in the metastatic disease cohorts. Subjects will be monitored for disease recurrence, but if recurrence occurs prior to the completion of blood draws or pheresis these tests can still be obtained if deemed valid by the PI.

Subjects in the metastatic disease cohort:

At the end of 8 weeks, we will allow tumor progression since patients will have only received vaccine at this point. We estimate that of a total of approximately 24 patients in this cohort, 17% will drop off at this point, leaving a total of 20 patients to be treated in Part 2. To have enough patients to evaluate the secondary endpoints, 20 additional patients may be enrolled in the metastatic disease cohort so that at least 30 patients (10/arm) with gel and 10 are available for Part 2.

At the end of 8 weeks of vaccine, cutaneous lesions (at least 2 and up to 10 lesions) will be assigned by the physician according to region to receive or not to receive 0.2% R848 gel. The CORe randomization system will not be used in Part 2. The physician will designate the regions and which tumors will be treated. The area of cutaneous lesions will be divided into two regions, Region A and Region B, striving to equalize tumor burden in each designated region as best as possible. When feasible, Region A will be a proximal group of lesions, and B distal. When this proximal – distal differentiation is not feasible because of the characteristics of the metastatic pattern, then A and B will be assigned to regions in no particular order. If the two regions coalesce during the vaccination phase, the coalesced tumor may be divided into two regions. Each target tumor whether it is treated or untreated will be marked, measured and photographed for the medical record. Because this dose provides the highest level of immune cell

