#### **9.6 Baseline measurement**

In this trial a period of immunization opens the treatment, and immunization alone mediates tumor response rarely. (Cancer immunotherapy: moving beyond current vaccines. Rosenberg SA, Yang JC, Restifo NP. *Nat Med.* 2004 Sep;10(9):909-15.) So with this sequence, as has been seen with other immunologic mediators, we should expect that a period of progression may precede any response from the treatment.

Therefore, because subjects are likely to progress during the vaccination portion of the study, the baseline will be that measurement during the first 10 weeks of the study at which the tumors are at their maximum size (based on sum of LD). Progression will be allowed during these first 10 weeks without withdrawal of the subject from treatment or from the study. This includes increase in the size of the lesions as well as the appearance of new lesions.

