A sample size argument for Part 2, based upon a 2-sample t-test (which represents a lower bound on the mixed-effects model given above), is as follows: we assume that a total of 24 patients will be enrolled in the metastatic disease cohort, and of these, 17% of the patients initially enrolled will discontinue the trial at 8 weeks due to progressive disease and that dropout will be equally distributed across the 2 arms, leaving a total of 20 patients (10/arm) for Part 2. The 2-sample t-test will assess differences in the change between the two treatment groups with respect to the 3 outcomes described previously. With 20 patients, we will have 80% power to detect an increase of 1.2 standard deviations in the R848 group for each outcome at 8 weeks, assuming a one-sided 2-sample t-test with a 5% Type I error rate. One of the benefits of our mixed-effects modeling approach is that it allows for the analysis of the data using complete likelihood methods (Beunckens, Molenberghs, and Kenward, 2005; Clinical Trials). In addition, we will perform 2 types of sensitivity analysis: 1) We will use last-observation-carried-forward; 2) We will explore how deviations from the Missing at Random (MAR)

assumption of the direct likelihood approach may impact inference using methods developed in Verbeke and Molenberghs (2000).

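### The 30 patients behind the Arm A + C response test appear to add a post-dropout count to an enrolment count, so n and the 82% power should be restated on one basis

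*Combined protocol and SAP*

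**What the plan says.** Section 11.0, Additional Cohort of Non-Randomized Patients, makes tumour response the main endpoint for Arm C: "Tumor response as measured by a 50% shrinkage in tumor size by irRC criteria will be the primary endpoint for these patients". It sets a standard-of-care rate of at most 5%, a target of 22%, and a one-sided exact binomial test at 5%. The sample size has two parts:

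- Arm A: "We expect a total of 10 metastatic disease patients in Arm A from the initial randomized portion of the trial".
- Arm C: "20 additional patients with metastatic disease will be enrolled into Arm C".

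The sum is used directly: "Combined with the additional 20 patients (Arm A and C, with a total of 30 patients, we will have 82% power".

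Section 11.0, Part 2, gives the only derivation of a figure of 10 metastatic patients per arm. It assumes 24 metastatic patients enrolled and that "17% of the patients initially enrolled will discontinue the trial at 8 weeks due to progressive disease", spread equally over the two arms, "leaving a total of 20 patients (10/arm) for Part 2". Section 6.0 gives the same 24-to-20 estimate. It then says that 20 more patients may be enrolled "so that at least 30 patients (10/arm) with gel and 10 are available for Part 2".

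**The concern.** The 10 for Arm A looks like a count of patients still present after week 8. The 20 for Arm C is a count at enrolment, with no loss applied, although Arm C has the same disease setting and the same vaccine plus R848 regimen. Section 6.0 goes further and treats all 20 enrolled Arm C patients as available for Part 2. If so, the 30 is neither the number enrolled nor the number expected to start Part 2, and the power quoted for Arm C's own endpoint belongs to neither set.

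No sentence names the denominator. The lowest-rank rule in Section 11.0, Part 1, covers only the T-cell rank test. The sensitivity analyses for missing data in Part 2 belong to the biopsy models. The crossover exclusion in Section 6.0 concerns clinical endpoints after week 24. Under Section 9.6, "the baseline will be that measurement during the first 10 weeks of the study at which the tumors are at their maximum size", so a patient who leaves at week 8 with progression has no later measurement to set against that baseline. Whether that patient stays in the denominator affects a small exact test, because the cut-off is a whole number of responders and moves with n.

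**Working it through.** **Inputs.** Null rate 0.05, target 0.22, one-sided exact binomial test at 0.05, 10 + 20 = 30 (Section 11.0, Additional Cohort). 24 metastatic patients enrolled and 17% lost at week 8 (Section 11.0, Part 2, and Section 6.0). The 17% for Arm C is an assumption; the plan gives no Arm C figure.

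**Rule.** The cut-off r is the smallest integer with P(X ≥ r | n, 0.05) ≤ 0.05. Power is P(X ≥ r) at the target rate.

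**1. The plan's figure.** At n = 30, P(X ≥ 4) = 0.0608 under the null, which is too large, and P(X ≥ 5) = 0.0156, so r = 5. Power = P(X ≥ 5 | 30, 0.22) = 0.821. The stated 82% is reproduced.

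**2. Counts on one basis.**
- Arm A: 24 / 2 = 12 enrolled; 12 × 0.83 = 9.96, or 10 after week 8.
- Arm C: 20 enrolled; 20 × 0.83 = 16.6 after week 8.
- Enrolled: 12 + 20 = 32.
- Reaching Part 2: 10 + 16.6 = 26.6, or about 26 to 27.

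**3. Cut-off by n (5% null).** P(X ≥ 4) is 0.0387 (n = 26), 0.0437 (27), 0.0491 (28), 0.0548 (29), 0.0608 (30) and 0.0738 (32). The cut-off therefore falls from 5 to 4 once n is 28 or fewer. If dropouts are excluded, two losses from Arm C are enough: 10 + 18 = 28.

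**4. Power under each reading.**

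| Set analysed | Cut-off | Exact error | Power |
|---|---|---|---|
| As stated, n = 30 | 5 | 0.0156 | 82.1% |
| Dropouts excluded, n = 26 | 4 | 0.0387 | 85.5% |
| Dropouts excluded, n = 27 | 4 | 0.0437 | 87.5% |
| All 32, 26 able to respond at 22% | 5 | 0.0204 | 70.7% |
| All 32, 27 able to respond at 22% | 5 | 0.0204 | 74.0% |
| All 32, 22% among all enrolled | 5 | 0.0204 | 86.3% |

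The error column applies the 5% null to the whole set in that row. With random rather than fixed dropout, the rate among all 32 is 0.22 × 0.83 = 0.183 and power is 72.0%, inside the 71-74% range.

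**5. Where the two denominators disagree.** With 27 reaching Part 2 and exactly 4 responders, 4/27 gives p = 0.044 and rejects; 4/32 gives p = 0.074 and does not. At 22% among the 27, the chance of exactly 4 is 0.8753 − 0.7397 = 0.136.

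**The case against.** Four arguments on the other side have weight.

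First, the plan never says that Arm A's 10 is a post-dropout figure. Arm C was added in April 2015, when randomised accrual was well advanced, so the 10 could be an accrual forecast and 10 + 20 a consistent enrolment count. This stands as a limit: the mixed basis is inferred. It remains the better reading, because 10 per arm is derived nowhere else, and there it is what is left of 12. The forecast reading also does not rescue Section 6.0, which counts 20 enrolled as 20 available.

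Second, the 17% is borrowed for Arm C, and Sections 9.6 and 10.1 let patients progress during the first 10 weeks without withdrawal. Actual loss may be lower. However, Section 6.0 gives its 17% estimate immediately after allowing progression, so the plan expected that loss despite the allowance.

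Third, Section 9.5 defines best response as a confirmed response and requires confirmation at least four weeks later. A patient who leaves at week 8 with no confirmed response therefore cannot be a responder. This stands in full: the numerator is clear, and only the denominator is open.

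Fourth, Arm C is a non-randomised addition outside the primary T-cell comparison. That limits the importance of the point but does not make the count right.

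A reader might go further and infer that the test is underpowered. The documents do not support this: two of the three readings give more than 82%, and the lower figure needs 22% to be the rate among patients reaching Part 2, which the plan does not say. A reader might also infer that leaving the denominator open inflates the type I error. If the 5% null applies to the 27 reaching Part 2, choosing the favourable rule afterwards rejects at 4 or more, with error 0.044, still below 5%. It reaches about 0.074 only if the null is applied to all 32 enrolled.

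**Conclusion.** The point holds as a correction to a stated sample size and power. On the plan's own assumptions, 30 is neither the number enrolled (about 32) nor the number expected to reach Part 2 (about 26 to 27). The 82% is correct arithmetic for n = 30 but describes neither set. Depending on the denominator and on what 22% refers to, power lies between about 71% and 88%, so it is misstated in no single direction. This rests on two assumptions: that Arm A's 10 is the count after week-8 loss, and that the 17% applies to Arm C.

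The missing denominator rule would, alone, be a matter of missing detail. It gains some weight here because the cut-off changes at n = 28, so the conclusion at exactly 4 responders depends on it.

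**What to change.** Before the response analysis, in Section 11.0 (Additional Cohort of Non-Randomized Patients):

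- Define the analysis set as all metastatic patients enrolled in Arms A and C, with those lacking a confirmed response counted as non-responders.
- Restate n as about 32, cut-off 5, exact error 0.020. If the final enrolled number differs, apply the same exact rule. The cut-off stays at 5 for any n from 29 (P(X ≥ 4) = 0.0548) to at least 37 (P(X ≥ 5) = 0.0359).
- Say which population the 22% refers to, and restate power as about 71-74% (patients reaching Part 2) or 86% (all enrolled).

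In Section 6.0, replace the 30 with about 26 to 27 expected to be available with gel, or label the 30 as making no allowance for Arm C dropout.

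The cost is a few sentences and no new data. The downside is that the stated power may be less favourable. Extra Arm C enrolment is not needed for this correction. Fixing the set in advance also settles how exactly 4 responders would be read.

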### **Overview of Analysis of Secondary Endpoints**

In addition to the Part 1 and Part 2 primary endpoints described above, several additional secondary endpoints will be investigated. Blood will be drawn at baseline, 2, 4, 8, 12, 16, 20, and 24 weeks, and every 4 weeks after the 24-week draw. A secondary analysis for data generated from Part 1 will measure *ex vivo* IFN- $\alpha$  via ELISPOT assay. This outcome is measured as a continuous variable. Our first step will be to plot each laboratory parameter over the 24 weeks of follow-up to visually inspect the data for any interesting trends between the two clinical trial arms. Separate graphical displays will be created for each treatment arm (gp100(g209-2M)/MAGE vaccine+R848 and gp100(g209-2M)/MAGE vaccine alone). Subsequent to the initial exploratory data analysis discussed above, a repeated measures model will be fit for each measured parameter in the blood to the data using Proc Mixed in SAS to model the repeated laboratory measurements over the 24 weeks of follow-up. Tumor biopsies will be taken as outlined in section 7.3. In addition, a punch biopsy will be taken at the vaccine site for all patients as outlined in section 7.3. To evaluate the ability of **locally administered** TLR agonist (R848 gel) to activate innate immune cells at the **vaccine site** we will evaluate the inflammatory microenvironment at the site of the immunization. Immune cell infiltration for pDCs, mDCs, NK cells, and T-cells will be measured along with immune cell function using IHC and quantitative RT-PCR (qRT-PCR) by Core B. For each patient, changes from baseline will be calculated for both the lesions treated with R848 and for the non-treated lesions. The 4 immune cell infiltration measures and qRT-PCR relative expression measures are all continuous variables. We will use Wilcoxon signed rank test to compare the measures between the lesions within patient. Significance will be assessed at the 5% level.

To evaluate the ability of R848 gel, administered at the tumor site to induce inflammation and up-regulation of adhesion molecules on tumor vasculature we will focus on the tumor biopsies taken in R848 treated and untreated tumors at pre and post-treatment timepoints outlined in section 7.3. These biopsies will be used to investigate the effect of R848 treatment on tumors compared to untreated tumors. We will measure inflammation and activation of tumor vasculature using Immuno-histochemistry (IHC) and flow cytometry (FACS). We will use mixed models to assess differences between treatment groups. Our mixed model will include fixed effects for treatments, and random effects for

time, treatment-by-time interaction and an additional random effect to model the within patient variability. Significance will be assessed at the 5% level.

To evaluate the ability of R848 gel, administered at the tumor site to enhance immune-cell infiltration into tumor we will utilize antibodies to PDC, mDC, NK, and T cells. Since these are continuous measures (assessed at baseline, 2, 4, 8, 12, 16, 20, and 24 weeks, and every 4 weeks after the 24-week draw) we will use mixed models to assess differences between treatment groups. Our mixed model will include fixed effects for treatments, and random effects for time, treatment-by-time interaction and an additional random effect to model the within patient variability. Significance will be assessed at the 5% level.

To evaluate the ability of R848 gel, administered at the tumor site to generate T-cells against additional tumor antigens, not present in the vaccine (i.e., antigen spreading) we will assess cytokine production against de novo antigens. Since these are continuous measures (assessed at baseline, 2, 4, 8, 12, 16, 20, and 24 weeks, and every 4 weeks after the 24-week draw) we will use mixed models to assess differences between treatment groups. Our mixed model will include fixed effects for treatments, and random effects for time, treatment-by-time interaction and an additional random effect to model the within patient variability. Significance will be assessed at the 5% level.

To evaluate the association between clinical response and laboratory parameters of T-cell priming, T-cell migration to tumor, and inflammation at the vaccine and tumor sites we will explore the relationship between immune cell activation measures at the vaccine site (vaccine site measures) and at the tumor site (tumor site measures). Additionally we will assess the effect of the TLR agonist R848 upon clinical response. Clinical response will be assessed using the immune-related response criteria (irRC) and will be assessed at week 8, 16, and every 8 weeks thereafter. Since both vaccine site measures and tumor site measures are continuous variables we will assess association between these two types of variables using Pearson's or Spearman's correlation coefficient. In addition, we will use logistic regression to model the relationship between either vaccine site or tumor measures and best clinical response assessed over a 16 weeks period after initial vaccination.

To assess the association between R848 treatment on lesions and response, the irRC will be used to assess response separately by lesion type (lesions receiving or not receiving R848 cream). That is, using the irRC, we will, for each patient, assess if the lesions not treated with R848 cream responded and also determine if the lesions treated with R848 cream responded. Thus, for each patient we will record 4 possible joint outcomes ++, +-, -+, and --, where the ++ indicates that both lesions receiving and not receiving R848 cream responded; -- indicates neither types of lesions responded. Similarly +- and -+ indicate one type of lesion responded while the other did not. We will assess differences between treatments (based on within patient differences) using McNemar's test. A statistically significant difference with respect to the McNemar's test will indicate if cream administered to the lesion results in improved outcome (i.e., immune-related response criteria) relative to lesions for which cream was not administered.

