### **6.0 Treatment Plan**

All patients will receive the class I, HLA-A2 restricted gp100(g209-2M) peptide vaccine. Patients who are HLA-DP4 positive will also receive the class II restricted MAGE-3 peptide, in separate extremities. This will allow us to generate melanoma-specific CD8+ and CD4+ T-cells. The gp100(g209-2M) immune response will be our primary endpoint for assessment of T-cell priming, since we have extensive previous experience with this vaccine and believe that CD8+ responses are critical to the development of a strong antitumor immune response. The MAGE-3 peptide will be given in order to stimulate antigen-specific CD4+ T-cells, which we believe are also important in the generation of strong antitumor immunity. Patients positive for both HLA types will

receive both vaccines, gp100(g209-2M) and MAGE-3, for eight weeks. Patients who are HLA-A2 positive and HLA-DP4 negative will receive only the gp100 peptide for 8 weeks. There will be two arms in Part 1: Arm A is the peptide vaccines plus the TLR7/8 agonist, R848 and Arm B is the peptide vaccines only. All patients will be randomized to either Arm A or Arm B by CORe during the registration process. The randomization will be stratified by cohort (metastatic disease or adjuvant). In Arm A, R848 gel will be applied to the gp100(g209-2M) vaccine injection site immediately following the injection. The R848 gel will be allowed to air dry for 30 minutes and then covered with a gauze dressing. All vaccines will be administered subcutaneously and intradermally. The gp100(g209-2M) peptide will be administered in the same extremity weekly (every 7 days +/- 2 days) for 8 weeks. Similarly, in a separate extremity of eligible patients, the MAGE-3 peptide will be administered weekly (every 7 days +/- 2 days) for 8 weeks. Each syringe (a total of 4, 2 for gp100 and 2 for MAGE-3) will contain 1ml of peptide vaccine; 0.5ml of the vaccine in each syringe will be administered intradermally and the other 0.5ml will be administered subcutaneously at each injection site for a total of 4 sites.

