**Vaccine biopsies:** Vaccine sites will be biopsied from all patients in the study when feasible. The vaccine site biopsied will be a GP100 vaccine site. The vaccine site will be identified and a punch biopsy taken of full thickness skin with standard sterile technique and closure. Vaccine sites will be biopsied at 24 hrs (+/- 6 hours) after the first gp100(g209-2M) vaccine and at week two of vaccination. These biopsies will occur the day following the vaccination for that week. Failure to obtain vaccine biopsies due to refusal, discretion of the investigators or infeasibility will not constitute a violation of the trial.

**Tumor biopsies** will be taken from patients in the cohort with metastatic disease. There will be no tumor biopsies in patients enrolled in the adjuvant cohort. The first

biopsy will be taken as a base line at any time after enrollment onto the trial, but prior to the first vaccination. A second tumor biopsy will be taken at week 8 prior to the first dose of R848 on the tumors, and at week 12 (4 weeks after initiating R848 therapy on the tumors, but at any time during that week) Tumors will be randomly selected when biopsied, but when feasible, a biopsy will be taken of both a treated lesion and untreated lesion at week 12. Tumor biopsies may be taken using any biopsy method to optimize tumor yield using standard sterile techniques. Tumor volume may not allow for all biopsies to be obtained in all individuals, in this case pre-vaccine biopsies and week 12 will take precedence. Tumor biopsies are at the option of the enrolled subject and the investigators, and failure to obtain tumor biopsies due to refusal, inadequate remaining tumor volume, discretion of the investigators or infeasibility will not constitute a violation of the trial.

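### Secondary objective A has no usable test: the vaccine-site analysis pairs treated and untreated lesions within patient, but R848 at that site differs only between arms and no baseline biopsy is taken

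*Combined protocol and SAP*

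**What the plan says.** Section 1.2 lists, as secondary objective A, whether locally applied R848 gel activates innate immune cells at the gp100 vaccine site. The analysis appears in section 11.0, Overview of Analysis of Secondary Endpoints. That paragraph restates the objective, names the measures (pDC, mDC, NK and T-cell infiltration, plus qRT-PCR expression), and continues: "For each patient, changes from baseline will be calculated for both the lesions treated with R848 and for the non-treated lesions". It then gives the test, "We will use Wilcoxon signed rank test to compare the measures between the lesions within patient", and the error rate, "Significance will be assessed at the 5% level", without saying whether that is one-sided or two-sided.

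The design is set out elsewhere:

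- **Allocation (section 6.0).** "Arm A is the peptide vaccines plus the TLR7/8 agonist, R848 and Arm B is the peptide vaccines only". On application: "In Arm A, R848 gel will be applied to the gp100(g209-2M) vaccine injection site immediately following the injection".
- **Site biopsied (section 7.3).** "The vaccine site biopsied will be a GP100 vaccine site".
- **Timing (section 7.3).** "Vaccine sites will be biopsied at 24 hrs (+/- 6 hours) after the first gp100(g209-2M) vaccine and at week two of vaccination".
- **Baseline (section 7.3).** A pre-vaccination baseline biopsy is scheduled for tumours only, and tumours are biopsied only in the metastatic cohort.

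**The concern.** A signed-rank test needs two values per patient that differ in the factor under study. At the vaccine site that factor is the gel, and a patient either has it there or does not, according to arm. The outcome is also defined as a change from a baseline that the biopsy schedule never collects.

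Objective A asks whether the gel has its intended local effect, which is the mechanism offered for better T-cell priming, the primary endpoint. A positive or negative primary result will be read in the light of this analysis. If the text stands, someone must choose the contrast, time point and sidedness after the data are in, across four cell types, several transcripts and two biopsy times.

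**Working it through.** The documents give no sample size or power for this analysis, so there is no stated figure to reproduce. The check is a count of what each patient can contribute, followed by the size of effect that the available comparison could detect.

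**1. Treated/untreated pairs at the biopsied site** (sections 6.0, 7.3 and 11.0)

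| | Patients | gp100 site with gel | gp100 site without gel | Pairs |
|---|---|---|---|---|
| Arm A | 24 | yes | none designated | 0 |
| Arm B | 24 | none | yes | 0 |
| Total | 48 | | | 0 |

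**2. Baseline values.** The two scheduled biopsies are at 24 hours after the first vaccine and on the day after the week-two vaccination. Both follow vaccination and, in Arm A, gel. There are 0 pre-treatment vaccine-site samples, so change from baseline cannot be computed.

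**3. Other possible sources of a pair**

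- *Second gp100 injection.* Section 6.0 describes two gp100 syringes, but no gp100 site in Arm A is reserved as gel-free.
- *MAGE-3 site.* It receives no gel, but it is not biopsied, carries a different peptide, and exists only in HLA-DP4-positive patients.
- *24 hours paired with week two.* This tests time, not R848.
- *Lesions read as tumours.* Gel reaches tumours only after week 8, after both vaccine-site biopsies. A tumour comparison does not address the vaccine site, and the adjuvant cohort would contribute nothing.

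**4. Any other test for objective A.** Section 7.2.2 only describes the staining. The repeated-measures model in section 11.0 is limited to blood parameters. The association analyses there are correlations and logistic regression. None compares vaccine-site measures between arms.

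**5. What the randomised comparison could detect.** The normal-approximation formula for 80% power is

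d = (z for alpha + 0.842) × √(2/n), divided by √0.955 for the rank-sum test (0.955 = 3/π).

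With n = 24 per arm:

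- Two-sided 5%: (1.96 + 0.842) × √(2/24) = 0.809; 0.809 / √0.955 = 0.83 SD.
- One-sided 5%: (1.645 + 0.842) × √(2/24) = 0.718; 0.718 / √0.955 = 0.73 SD.

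Replacing the normal approximation by the noncentral t raises these slightly. Vaccine-site biopsies are optional and the documents give no completion rate, so the lower rows are assumptions.

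| Biopsied per arm | One-sided 5% | Two-sided 5% |
|---|---|---|
| 24 (all) | 0.75 SD | 0.85 SD |
| 18 (75%) | 0.87 SD | 0.98 SD |
| 12 (50%) | 1.07 SD | 1.22 SD |

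**6. Orientation against the Part 1 claim.** Section 11.0 states 80% power for 0.73 SD with 24 per arm at one-sided 0.05. The same methods, ignoring the interim look, give 81.2% (normal approximation), 80.1% (noncentral t) and 79.6% (normal approximation with the rank efficiency factor). The plan's figure reproduces.

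**The case against.** The strongest reply is that the two sentences are tumour text in the wrong place. In sections 6.0 and 11.0, lesions treated or not treated with R848 are tumours, and tumour biopsies are mentioned just before the vaccine-site text. On that reading the signed-rank test can be computed, with up to about 20 metastatic patients in Part 2, and the count of 0 pairs does not apply to it. This is plausible as an account of how the error arose. It does not supply a test for objective A: the defect becomes a missing analysis instead of an impossible one. It would also duplicate tumour analyses that section 11.0 already gives under Part 2 and in the tumour-site paragraphs.

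A second reply is that the intended contrast can be inferred, because section 7.2.2 speaks of assessing vaccine-site infiltrate with and without TLR agonist. At the gp100 site that can only mean Arm A against Arm B. True, but no test, time point or sidedness is named.

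Third, the matter is secondary. The primary Part 1 rank-sum comparison and the Part 2 primary analysis do not depend on it, and no data are lost. That stands and limits the consequence to objective A. It is also fair that a between-arm repeated-measures model would serve as well as a rank test. What the design compels is the between-arm contrast, not the particular statistic.

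**Conclusion.** The concern holds. As written, the vaccine-site analysis has neither the pairs nor the baseline it requires, and no other passage tests the effect of R848 at that site. The defect lies in the analysis text, not in the design: the randomisation and planned biopsies support an unbiased between-arm comparison, provided missingness of the optional biopsies is not related to arm and outcome.

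The detectable effects above assume approximately normal outcomes, one measure at one time point, no multiplicity adjustment, and an unstratified test. They are moderate to large effects even with complete biopsies, so the result should be reported with interval estimates. A named objective that cannot be analysed as stated must be corrected before the vaccine-site data are examined.

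**What to change.** Replace the change-from-baseline and signed-rank sentences for the vaccine site with the following:

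- **Comparison.** Arm A versus Arm B by Wilcoxon rank-sum test stratified by cohort (van Elteren), on observed values, for pDC, mDC, NK and T cells and each qRT-PCR measure.
- **Time points.** Analyse the 24-hour and week-two biopsies separately and say which one leads.
- **Error rate.** State one-sided or two-sided 5%. Four cell measures at two times already make 4 × 2 = 8 tests before qRT-PCR, so either name a lead measure or label the set exploratory.
- **Missing biopsies.** Report the number obtained by arm and time with reasons, and state how missing values are handled.
- **Arm C.** State that the 20 non-randomised patients, all of whom receive R848, are outside this comparison. Their vaccine sites may be biopsied under section 7.3, so the point should not be left open.
- **Tumour lesions.** Keep paired within-patient tests for these only, in the tumour-site text.

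The cost is wording. Because the analysis plan sits in the protocol, section 13.1 requires a written amendment with IRB approval. No visit, biopsy or assay is added.
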